Secondary: Assess the effect of Belatacept conversion in the percent change of renal function from baseline to 12 months; donor-specific anti-HLA antibodies presence and intensity (MFI); correlation of B7-1 positivity on immunofluorescence on biopsy with B7-1-expression in urine extracellular vesicles; adverse events; acute rejection episodes; blood pressure control; new onset diabetes; hyperlipidemia; graft survival; and patient survival.

Study design:

Inclusion Criteria:

1. Male or female adult kidney transplant recipients older than 18 years old
2. eGFR $\geq 30\text{ ml/min}$
3. ≥ 6 months after transplantation
4. Proteinuria $\geq 1\text{ gram/day}$ in spot urine protein/creatinine ratio
5. Available biopsy specimen for B7-1 staining at recruitment time.
6. Ability to provide written informed consent for the study.
7. Maintenance immunosuppression of CNI (cyclosporine or tacrolimus), antiproliferative agent (azathioprine, MMF or MPA) with either steroids or not.
8. Must be EBV IgG positive

Exclusion Criteria:

1. Age < 18 years

2. eGFR<30 ml/min
3. active acute cellular rejection (ACR; higher than borderline) or ACR in the previous 6 months; active acute antibody-mediated rejection.
4. recurrent FSGS
5. EBV IgG negative
6. patient on mTOR inhibitor (e.g. Everolimus, Sirolimus)
7. patient only on CNI (cyclosporine or tacrolimus) and steroids

Accrual Goal: 36 subjects, 3 study sites

Accrual Rate: approximately 2 subjects/month; total of 18 months enrollment; 18 months of follow-up

First Patient First Visit: 1-March-2015

Statistics: This is a Phase I clinical trial to test the safety and gain further insight into the potential effect of Belatacept in proteinuric kidney transplant patients. We plan to recruit 36 patients, based on the feasibility for recruitment in 3 transplant centers and prior literature on recommended sample sizes in a Phase I trial.

2. Background:

Although improvements in immunosuppression have led to a reduction in acute rejection rates, long-term allograft survival remains disappointing, with more than 50% of allografts lost 10 years after transplantation.

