Proteinuria develops in about **30% of kidney transplant recipients** and is **strong predictor of graft loss** (1-3). The amount of proteinuria has a direct correlation with the risk of graft failure (**Figure 1**). More than 80% of patients with proteinuria greater than 1500 mg/d have evidence of allograft glomerular pathology. Among these, transplant glomerulopathy is the leading etiology in about 45% of cases followed by recurrent glomerular disease (25%) (4, 5). Patients with more than 1 gram/day of proteinuria after transplantation carry a dismal prognosis more than 50% of grafts lost after a mean follow up of 5 years (4). The proteinuria on these patients continues to progress and kidney function deteriorates until grafts are lost with no effective therapy to halt this progression, therefore the need to establish novel therapies for this subset of transplant patients.

KDIGO guidelines recommend ACEI/ARB in post-transplant proteinuric patients though there is no clear evidence that this approach improves renal transplant survival (6, 7). In contrary, ACEI/ARB have been associated with significant decrease in renal function, anemia and hyperkalemia post-transplantation. Novel therapies are urgently needed to reduce proteinuria and prevent graft loss in transplant recipients.

It has been recently published that **Abatacept is able to reduce proteinuria in patients with B7-1-positive glomerular disease** by stabilizing β 1-integrin activation in podocytes (8). However, prevalence of positive B7-1 staining in renal allografts and a possible role of B7-1 target therapy in the treatment of proteinuria post-transplantation remains to be explored.

3. Preliminary Data:

[figure not shown]

Figure 1. Risk of graft failure according to degree of proteinuria.

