Using a goat anti-human B7-1 (CD80) antibody, we performed immunostaining for B7-1 on frozen sections of **123 clinically indicated kidney transplant biopsies** obtained between 2011 and 2012. Fifteen patients had $\geq 1+$ B7-1 staining on glomeruli at podocyte location (**Figure 2**). The predominant pathologic diagnosis among those with B7-1 positivity was **transplant glomerulopathy** (46%). In addition, 27% of patients with $\geq 1+$ B7-1 staining in their biopsies had nephrotic range proteinuria (4 out of 15) and 50% of allograft biopsies obtained from patients with nephrotic syndrome stained positive for B7-1 (4 out of 8). In sum, **B7-1 is expressed at significant levels in about 10% of kidney allograft biopsies.**

[figure not shown]

Figure 2. B7-1 staining in kidney transplant biopsies.

4. Hypothesis:

We hypothesize that B7-1 targeting therapy may reduce proteinuria and improve graft survival in proteinuric transplant recipients that have B7-1 staining on allografts. In addition, the absence of CNI nephrotoxicity and the potential protective effect of Belatacept on DSA production may be of benefit in this subset of transplant patients (9, 10).

5. Objectives:

Primary: Determine the effect of Belatacept conversion in reducing proteinuria by 25% at 12 months in renal transplant recipients that have more than 1 gram of proteinuria per day and are either B7-1-positive or negative on kidney biopsy.

Secondary: Assess the effect of Belatacept conversion in the percent change of renal function from baseline to 12 months; donor-specific anti-HLA antibodies presence and intensity (MFI); correlation of B7-1 positivity on immunofluorescence on biopsy with B7-1-expression in urine extracellular vesicles; adverse events; acute rejection episodes; blood pressure control; new onset diabetes; hyperlipidemia; graft survival; and patient survival.

6. Proposal:

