We propose to perform a multi-center study in which adult kidney transplant recipients with proteinuria (≥ 1 g/day) will be converted from CNI to Belatacept (**Figure 3**) once B7-1 staining has been performed on allograft biopsy ([name] will be performing all stains). This is a Phase I study that will aim to enroll 36 patients in 18-month recruitment time involving 3 transplant sites. Other inclusion criteria include: eGFR > 30 ml/min, greater than 6 months post-transplant and EBV IgG positive status. **Exclusion criteria** include: age < 18 years, eGFR < 30 ml/min, active acute cellular rejection (ACR; higher than borderline) or ACR in the previous 6 months, recurrent FSGS, EBV IgG negative status and on mTOR inhibitor as maintenance immunosuppression.

[figure not shown]

Figure 3. Study Design. Protocol and outcomes measures are detailed.

Patients that develop proteinuria after transplant are a heterogenous group with many potential

underlying etiologies including calcineurin inhibitor toxicity, transplant glomerulopathy, BK nephropathy or recurrent glomerular disease (4). Therefore, we decided to enroll 12 patients per center (3 centers total) to allow the inclusion of different etiologies of proteinuria and be a feasible study based on our inclusion criteria.

By including both B7-1 positive and B7-1 negative patients with proteinuria in the study, we will have the best chance of success and it would also allow for future testing for other potential prognostic markers in this population. One of the main reasoning's behind this is that the B7-1 staining is undergoing further optimization by [name] and a NIH task force, and therefore, restricting our recruitment may limit interpretation of the data in case the staining changes. This has been previously shown to be most productive approach in biomarker-driven interventions in the cancer field (11). In addition, the exact mechanism in which B7-1 targeting reduce proteinuria is still debated. By including both B7-1 positive and B7-1 negative patients with proteinuria, we will be able to assess overall risk factors and have a control group with no B7-1 staining treated with Belatacept. A historical control group with patients that fit the inclusion criteria and were managed as standard of care at our institution will also be included for comparison.

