10.7 Potential Drug Induced Liver Injury (DILI)

Specific criteria for identifying potential DILI have not been identified for this protocol. Standard medical practice in identifying and monitoring hepatic issues should be followed.

Wherever possible, timely confirmation of initial liver-related laboratory abnormalities should occur prior to the reporting of a potential DILI event. All occurrences of potential DILIs, meeting the defined criteria, must be reported as SAEs (see Section 10.9 for reporting details).

Potential drug induced liver injury is defined as:

1. AT (ALT or AST) elevation > 3 times upper limit of normal (ULN),
AND
2. Total bilirubin > 2 times ULN, without initial findings of cholestasis (elevated serum alkaline phosphatase),
AND
3. No other immediately apparent possible causes of AT elevation and hyperbilirubinemia, including, but not limited to, viral hepatitis, pre-existing chronic or acute liver disease, or the administration of other drug(s) known to be hepatotoxic.

Wherever possible, timely confirmation of initial liver-related laboratory abnormalities should occur prior to the reporting of a potential DILI event. All occurrences of potential DILIs, meeting the defined criteria, must be reported as SAEs (see Section 10.9 for reporting details).

Potential drug induced liver injury is defined as: [can be defined based on specific study]

10.8 Data Monitoring Committee, Data and Protocol Compliance Monitoring, and Other External Committees Please see MOP for information, including how often a site must complete their electronic clinical research forms (eCRFs), query resolution guidelines, regulatory binder requirements, and how the study data, and protocol compliance, will be monitored by the Sponsor ([name]/designated study managers).

11. Statistics: This is a phase I clinical trial to test the safety and gain further insight to the potential effect of Belatacept in proteinuric patients. We plan to recruit 36 patients, based on the feasibility for recruitment in 3 transplant centers and prior literature on recommended sample sizes in Phase I trials.

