The primary endpoint of the study will be a 25% reduction in proteinuria from baseline to 12 months. This endpoint was extrapolated from studies with ACE inhibitors showing significant benefit in patients with kidney disease and proteinuria that reached this endpoint (12). For comparison, we will also have a historical control group with patients that fit the inclusion criteria and were managed as standard of practice on our institution. A logistic regression model will be used to control for key variables such as baseline ACEI/ARB use, level of proteinuria, age and gender.

For the primary endpoint: Percentage of those patients who have a $\geq 25\%$ reduction in proteinuria from baseline to 12 months will be reported separately for each group. We will compare these percentages between the two groups using Fisher's exact test. In addition, means and standard deviations of the actual reduction will be reported separately for each group and will be compared between the two groups using a non-parametric test (Wilcoxon rank-sum). These results will also be compared to historical controls. A logistic regression model will be used to control for key variables such as baseline ACEI/ARB use, level of proteinuria, age and gender.

For the secondary endpoints: Descriptive statistics (means, standard deviations and/or percentages) will be reported on percent change of renal function from baseline to 12 months; donor-specific anti-HLA antibodies presence and intensity (MFI); adverse events; acute rejection episodes; blood pressure control; new onset diabetes; and hyperlipidemia. Spearman correlations will be calculated between B7-1 positivity on immunofluorescence on biopsy with B7-1-expression in urine extracellular vesicles. Kaplan-Meyer plots will be used to study graft survival and patient survival and a proportional hazards model will be used here to compare survival between treated and historical controls, controlling for the baseline covariates above.

References:

2. Halimi J-M. Low-grade proteinuria and microalbuminuria in renal transplantation. *Transplantation*. 2013;96(2):121-30.

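### Historical controls are not selected, described or adjusted by biopsy diagnosis, so the treated-versus-historical comparisons can reflect diagnosis mix

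*Combined protocol and SAP*

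**What the plan says.** **Mixed causes are intended.** Section 6 calls proteinuric recipients heterogeneous and names CNI toxicity, transplant glomerulopathy, BK nephropathy and recurrent glomerular disease. It gives as one reason for the enrolment plan "to allow the inclusion of different etiologies of proteinuria". The Synopsis states "Accrual Goal: 36 subjects, 3 study sites".

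**Historical controls.** Sections 6 and 11 describe them as patients who meet the inclusion criteria and had usual care at a single institution. Their number, period and method of selection are not given. Section 7.1 requires a biopsy specimen for staining but no particular diagnosis. Recurrent FSGS, active rejection and cellular rejection in the previous 6 months are listed under exclusion (Section 7.2), and the description of the controls does not mention exclusion criteria.

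**Analysis.** Section 11 compares the proportion with at least a 25% reduction in proteinuria, and the size of the reduction, between two groups and then with the historical controls. A logistic model is to "control for key variables such as baseline ACEI/ARB use, level of proteinuria, age and gender". A proportional hazards model for survival, treated versus historical, uses the same covariates. Diagnosis is not named as a covariate, stratum, subgroup or descriptive item, and the Schedule of Events has no entry for it.

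**The concern.** There is no randomised comparator, so the historical group is the only reference in the plan that did not receive belatacept. The comparison is fair only if the two groups would have fared alike under the same care. The protocol itself says that the condition has several distinct causes, and it is reasonable to expect proteinuria and graft survival to follow different courses in them.

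Two features make an unequal mix likely enough to plan for. Treated patients come from three centres and controls from one. Also, read literally, the controls could include recurrent FSGS or recent rejection, which the treated group cannot. Adjusting for age, gender, ACEI/ARB use and proteinuria level does not correct for cause. At stake is whether a difference from historical controls can be credited to conversion, or whether a lack of difference hides an effect.

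**Working it through.** **1. The plan's own figure.** 12 per centre × 3 centres = 36, and 2 per month × 18 months = 36. Both agree with the stated 36. No significance level, power or effect size is given, so there is no power calculation to reproduce.

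**2. Size of the case-mix difference.** If treatment has no effect and patients fall into two diagnosis classes:

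spurious difference = (gap in diagnosis share) × (gap in response between diagnoses)

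Both gaps are assumptions; the documents give neither.

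| Share gap | Response gap 20 points | 30 points | 40 points |
|---|---|---|---|
| 10 points | 2 | 3 | 4 |
| 20 points | 4 | 6 | 8 |
| 30 points | 6 | 9 | 12 |

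The range is 2 to 12 percentage points.

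**3. Effect on a test against historical controls.** Assume 10% response in transplant glomerulopathy, 40% otherwise, no treatment effect, and a two-sided 5% Fisher test with 36 treated versus 36 or 72 controls. Starting from the 46% transplant glomerulopathy share in Section 3, the group response rates are:
- share 46%: 0.46 × 10 + 0.54 × 40 = 26.2%
- share 26%: 0.26 × 10 + 0.74 × 40 = 32.2%
- share 16%: 0.16 × 10 + 0.84 × 40 = 35.2%

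Exact probability of a significant result:

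| Share, treated vs control | 36 vs 36 | 36 vs 72 |
|---|---|---|
| 46% vs 46% | 2.7% | 3.7% |
| 26% vs 46% | 5.3% | 8.5% |
| 16% vs 46% | 8.5% | 14.1% |

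A 30-point gap multiplies the false-positive rate by 8.5/2.7 = 3.1 or 14.1/3.7 = 3.8. Adding controls makes it worse, because the bias does not shrink with numbers.

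**4. The same check on B7-1 positive versus negative.** Section 3 found 15 of 123 biopsies positive (12.2%; the text says about 10%), so 36 patients would give 3.6 to 4.4 positives. At the 50% seen in nephrotic patients (4 of 8) there would be 18. With shares of 16% vs 46%, the rejection rate is 4.1% for 4 vs 32 and 4.5% for 18 vs 18. These are below 5% mainly because the groups are small; the formula in step 2 applies equally.

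Whether diagnosis differs by B7-1 status is a separate question. In Section 3, "The predominant pathologic diagnosis among those with B7-1 positivity was" transplant glomerulopathy, at 46%. This fits 7 of 15 (exact 95% interval 21% to 73%). Section 2 gives about 45% among proteinuric recipients with glomerular pathology. No share is given for B7-1-negative biopsies.

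**5. Room for model adjustment.** With 36 treated, an assumed 36 controls and an assumed 30% response, there are 72 × 0.30 = 21.6 responders. Group plus four covariates gives 21.6/5 = 4.3 per parameter, one diagnosis term gives 21.6/6 = 3.6, and three cause indicators give 21.6/8 = 2.7. Among the 36 treated alone, 10.8/5 = 2.2 falls to 10.8/8 = 1.4 with three indicators.

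**The case against.** The best defence is scale and purpose. This is a Phase I study whose size is "based on the feasibility for recruitment in 3 transplant centers and prior literature on recommended sample sizes in Phase I trials", meant to test safety and give early insight. At 30% response, the 95% half-width for 36 vs 36 is 1.96 × √(0.21 × 2/36) = 21 points, larger than any bias in the grid, and every input to that grid is assumed. This stands as a limit on how much weight any comparison can carry. It does not excuse a control group chosen without regard to cause, since the plan still specifies tests and adjusted models against it.

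The covariate list is open-ended, medical history is taken at screening, and the eCRFs and manual of procedures are not part of these documents. Diagnosis may therefore be collected and could be added later. That is fair, but nothing is prespecified, and neither point governs how controls are chosen. The sponsor may also intend the exclusion criteria to apply to controls; the text does not say so.

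A reader might go further and infer that the B7-1 comparison is itself confounded by diagnosis: positives carry transplant glomerulopathy, negatives carry CNI toxicity and improve because CNI is stopped, and a B7-1 effect is masked or reversed. The documents do not support this. The 46% among positives is close to the 45% background figure, and there is no figure for negatives. Section 4 offers absence of CNI nephrotoxicity as a possible benefit for these patients generally, not only for those diagnosed with CNI toxicity. The association that the preliminary data do suggest is with nephrotic-range proteinuria, and proteinuria level is already a covariate.

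**Conclusion.** The concern holds for the treated-versus-historical comparisons of proteinuria response and survival. Causes are mixed by design, controls are neither selected nor compared by diagnosis, the exclusion criteria are not said to bind them, and the named covariates leave the gap open. The bias could be 2 to 12 percentage points in response, in either direction, under assumed share gaps of 10 to 30 points and response gaps of 20 to 40 points. The false-positive rates of 8.5% and 14.1% also rest on assumed response rates, control numbers, test and significance level. No size can be given for survival.

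For B7-1 positive versus negative, a link with diagnosis is possible but not shown. It justifies describing diagnosis by B7-1 group, not a claim that the contrast is biased.

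**What to change.** In Sections 6 and 11:

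1. Record one broad diagnosis category from the existing biopsy report for every treated patient and every historical control.
2. State that controls must meet the exclusion criteria as well as the inclusion criteria.
3. Select or frequency-match controls on a broad category, for example transplant glomerulopathy versus other.
4. Tabulate diagnosis by B7-1 group and for controls, and show response by diagnosis descriptively.
5. Keep the sponsor's covariates. Label any model adjustment for diagnosis an exploratory sensitivity analysis, since there would be only about 3.6 responders per parameter even with one added term. Exchanging a named covariate for transplant glomerulopathy yes/no is not advised: that term pools CNI toxicity with the other causes and would not separate the effect of stopping CNI.

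The cost is one data field, a chart-review item for controls and a few lines of text. Charts without a biopsy diagnosis cannot serve as controls, so the pool, whose size is not stated, may shrink. The criterion of an available specimen already limits that loss, although it does not guarantee a single recorded diagnosis.

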7.3 Age and Reproductive Status

- Women of childbearing potential (WOCBP) must have a negative serum or urine pregnancy test (minimum sensitivity 25 IU/L or equivalent units of HCG) within 24 hours prior to the start of study drug.
- Women must not be breastfeeding
- WOCBP and male subjects with reproductive potential must agree to follow instructions for method(s) of contraception for the duration of treatment with study drug and for four (4) months post-treatment completion.
- Azoospermic males and WOCBP who are continuously not heterosexually active are exempt from contraceptive requirements. However, they must still undergo pregnancy testing as described in this section.

Investigators shall counsel WOCBP and male subjects who are sexually active with WOCBP on the importance of pregnancy prevention and the implications of an unexpected pregnancy. Investigators shall advise WOCBP and male subjects who are sexually active with WOCBP on the use of highly effective methods of contraception.

Highly effective methods of contraception have a failure rate of < 1% when used consistently and correctly.

At a minimum, subjects must agree to the use of one method of highly effective contraception as listed below:

7.4 HIGHLY EFFECTIVE METHODS OF CONTRACEPTION

- Male condoms with spermicide
- Hormonal methods of contraception including combined oral contraceptive pills, vaginal ring, injectables, implants and intrauterine devices (IUDs) such as Mirena[□] by WOCBP subject or male subject's WOCBP partner
- Female partners of male subjects participating in the study may use hormone-based contraceptives as one of the acceptable methods of contraception since they will not be receiving study drug
- IUDs, such as ParaGard[□]
- Tubal ligation
- Vasectomy.
- Complete Abstinence*

*Complete abstinence is defined as complete avoidance of heterosexual intercourse and is an acceptable form of contraception for all study drugs. Female subjects must continue to have pregnancy tests. Acceptable alternate methods of highly effective contraception must be discussed in the event that the subject chooses to forego complete abstinence

At a minimum, subjects must agree to the use of two methods of contraception, with one method being highly effective and the other method being either highly effective or less effective as listed below:

7.5 LESS EFFECTIVE METHODS OF CONTRACEPTION

- Diaphragm with spermicide

- Cervical cap with spermicide
- Vaginal sponge
- Male Condom without spermicide
- Progestin only pills by WOCBP subject or male subject's WOCBP partner
- Female Condom*.

* A male and female condom must not be used together

8. Study Drug: Belatacept (Treatment with Belatacept will continue for 12 months)**:

Belatacept conversion dosing: 5 mg/kg IV on days 1, 15, 29, 43 and 57, followed by an infusion every 28 days thereafter. Calcineurin inhibitors (CNI) Taper: CNI dose will remain the same for week 1 and then will be tapered by 25% each week and discontinued at the end of week 4 (day 29).

Infusion pre-medications: none

Duration of Infusion: 30 minutes

Observation period post-infusion: none

Standard of Care (SOC) Dosing of Belatacept:

5 x the patient's weight (in kg) = mg of Belatacept. Dose then needs to be rounded to the nearest 12.5 mg increment. Example: 74 kg patient x 5 = 370 mg; rounded to the nearest 12.5 mg increment = 375 mg. At the end of 12 months, study subjects have completed the study drug protocol and they have the option to continue on Belatacept treatment, paid for by their medical insurance, or they can switch back to a CNI.

**Please see additional important study drug information on pages 11-12.

